8.1.2.3. End of Treatment Visit

The End of Treatment Visit procedures described below will be the same for all subjects, regardless of phase. Subjects should return to the study site for an End of Treatment Visit within approximately 7 days after determination of disease progression or within 7 days after treatment discontinuation of PEGPH20 and pembrolizumab for other reasons. AEs and concomitant medications will be obtained and the following procedures should be performed:

- Perform the following assessments: physical examination including vital signs, ECOG Performance Status and 12-lead ECG.
- Obtain CT/MRI scan and send to CIV for storage (CT/MRI should only be done if radiographic disease progression was not documented in the previous CT/MRI scan).
- Obtain samples for the following tests and send to the central laboratory: hematology, blood chemistry and coagulation.
- Obtain sample for immunogenicity testing and send to the central laboratory.

8.1.2.4. Long-Term Follow-Up

After the End of Treatment Visit, all subjects will enter long-term follow-up during which information on the subject's survival status and subsequent anti-cancer therapies (i.e., therapies received, responses) will be obtained by the site once every 12 weeks. Long-term follow-up will continue until the subject dies, is lost to follow-up, or withdraws consent.

8.1.3. Procedures for Study Treatment Discontinuation

In the event of study treatment discontinuation, the subject should be instructed to report to the clinic as early as possible after the decision to discontinue study treatment has been made or for the next scheduled clinic visit. When the subject returns to the clinic, all End of Treatment procedures should be conducted (see Section 8.1.2.3). The Investigator will make his or her best efforts to perform these procedures.

8.2. Study Assessments

8.2.1. Informed Consent

The Investigator or designee must present and explain the study protocol to prospective study subjects before screening. The Investigator or designee must be available to answer any questions the subject may have regarding the study protocol and procedures. The Investigator or designee must explain that the subject is not obliged to enter the study and is free to withdraw from it at any time for any reason. If new safety information becomes available and results in significant changes in risk/benefit assessment, the ICF should be reviewed and updated if necessary. Under this circumstance, all subjects, including those already being treated, should be given the new information, given a copy of the revised ICF, and allowed to re-evaluate their consent to continue in the study.

A copy of the signed and dated ICF will be provided to the subject. The original ICF will be retained by the Investigator.

8.2.1.1. Prescreening Informed Consent in Dose Expansion

In accordance with local policies and institutional guidelines, subjects may provide consent for their tumor tissue to undergo HA testing on a separate, prescreening ICF. **Note:** If the subject provides consent to participate in the study and undergoes the remaining screening procedures, the 28-day screening window will begin when the subject signs the study ICF (i.e., signature on a prescreening ICF does not initiate the screening window).

8.2.2. Inclusion/Exclusion Criteria

The inclusion/exclusion criteria (Sections 7.1 and 7.2) must be reviewed at screening to ensure that the subject qualifies for the study. Subjects may be enrolled into the study if all selection criteria are met.

8.2.3. Medical History

A complete medical history (significant past and ongoing conditions), tobacco/nicotine usage history and demographic information will be obtained at screening. Previous history of allergies/allergic reactions (e.g., allergy to bee stings, anaphylaxis, etc.) should also be captured on the Medical History eCRF page.

8.2.4. Concomitant Medications

Information regarding collection of concomitant medications is provided in Section 10.12.

8.2.5. Adverse Events

AEs will be collected as defined in Section 10.

8.2.6. Physical Examination

Physical examination, including head/ears/eyes/nose/throat, respiratory, cardiovascular, gastrointestinal, musculoskeletal, central and peripheral nervous system, and dermatologic assessments, will be performed when required by protocol.

8.2.7. Height and Weight

Height will be recorded in cm, and weight will be recorded in kg.

8.2.8. ECOG Performance Status

The subject's ECOG Performance Status will be assessed (see Appendix B).

8.2.9. Vital Signs

Assessment of vital signs includes the measurement of blood pressure (systolic and diastolic), pulse, respiratory rate, and body temperature. Blood pressure and pulse will be measured with the subject at rest and in a sitting position for at least 5 minutes.

8.2.10. 12-lead ECG

ECGs including clinical significance will be evaluated by the Investigator and recorded in the eCRF.

8.2.11. Hematology, Blood Chemistry, Glucose, Thyroid Hormones, Coagulation Parameters, and Urinalysis

Hematology, blood chemistry, blood glucose, thyroid hormones, coagulation parameters, and urinalysis will all be analyzed by the central laboratory. In addition, local laboratories may be used if immediate clinical decision making is required (e.g., for measurement of liver function, including total bilirubin, ALP, AST and ALT prior to dosing [within 48 hours is acceptable] during Cycle 1 through Day 1 of Cycle 2 [Table 2 and Section 8.1.2]). For study analysis and reporting purposes, only values derived from the central laboratories will be utilized. The Investigator must evaluate all results outside the reference range and determine the clinical significance (clinically significant or not clinically significant).

- Hematology: hemoglobin, hematocrit, red blood cell count, white blood cell (WBC) count, neutrophils (ANC), lymphocytes (absolute), monocytes (absolute), eosinophils (absolute), basophils (absolute), granulocytes (absolute), mean corpuscular hemoglobin, mean corpuscular volume, and platelet count.
- Blood chemistry: glucose, blood urea nitrogen (BUN), albumin, total bilirubin, alkaline phosphatase, AST, ALT, electrolytes (including sodium, potassium, calcium, magnesium, chloride, and bicarbonate), and creatinine.
- Since the pembrolizumab Prescribing Information (Keytruda® US Prescribing Information 2017) advises monitoring of patients for hyperglycemia or other signs and symptoms of diabetes, blood glucose will be monitored throughout the study as either part of the chemistry panel or as a single assessment (see Schedule of Events Table 1 and Table 2).
- Since the pembrolizumab Prescribing Information (Keytruda® US Prescribing Information 2017) advises monitoring of patients for changes in thyroid function at the start of treatment and periodically during treatment, the thyroid hormones free triiodothyronine (T3); free total thyroxine (T4), and thyroid stimulating hormone (TSH) will be monitored throughout the study (see Schedule of Events Table 1 and Table 2).
- Coagulation: international normalized ratio (INR), prothrombin time (PT), and partial thromboplastin time (PTT).
- Urinalysis: protein, glucose, ketones, blood, specific gravity, nitrite, pH, and leukocytes.

8.2.12. Pregnancy Test

A serum or urine human chorionic gonadotropin test to determine whether a female subject is pregnant should be collected for all WOCBP. A woman is considered of childbearing potential, i.e. fertile, following menarche and until becoming post-menopausal unless permanently sterile. A postmenopausal state is defined as no menses for 12 months without an alternative medical

cause. Permanent sterilization methods include hysterectomy, bilateral salpingectomy and bilateral oophorectomy. The pregnancy test will be done by the local laboratory within 7 days before Day 1 (first dose of study medication). Pregnancy tests will be performed approximately every month at the beginning of each treatment cycle (Cycles 2 and beyond) during the study.

8.2.13. Contraception

Highly effective methods of contraception for participating WOCBP should be used during the study treatment and up to 4 months following the last dose of any study medication, and include the following:

- Combined (estrogen and progestogen containing) hormonal contraception associated with inhibition of ovulation (oral, intravaginal, transdermal)
- Progestogen-only hormonal contraception associated with inhibition of ovulation (oral, injectable, implantable)
- Intrauterine device
- Intrauterine hormone-releasing system
- Bilateral tubal occlusion
- Vasectomized partner

Participating men can be fertile or vasectomized. Fertile men are advised to use effective methods of contraception during the study and until 3 months after administration of the last dose of any study medication.

8.2.14. Immunogenicity

A blood sample will be collected from all subjects who receive PEGPH20 and analyzed to determine if PEGPH20 is eliciting a humoral immune response. Initial anti-drug antibodies (ADA) testing will be done using a multi-tiered approach per the Guidance, and immunocompetition will be performed to confirm an initial positive response in the screening assay. Any samples confirmed as positive in the ADA assay will then be assayed for neutralizing antibodies.

Refer to the Prescribing information of pembrolizumab for information related to immunogenicity of pembrolizumab (Keytruda® US Prescribing Information 2017).

8.2.15. Imaging/Radiologic Evaluation

CT/MRI with contrast evaluations will be performed for all subjects in accordance with each site's Standard of Care Lung or Gastric Adenocarcinoma CT/MRI imaging protocols (include chest, abdomen, pelvis contrast-enhanced CT/MRI). CT/MRI scans of other areas of known or newly suspected disease must also be obtained. In the event that the subject is intolerant to any contrast agents needed for imaging, local/institutional guidelines should be followed for imaging evaluation.

All scans will be evaluated locally for disease assessment using RECIST v1.1 and irRC, and sent to the CIV for storage and possible analysis at the end of the study.

For study eligibility, the Investigator must determine the presence of 1 or more tumors based on CT/MRI scans performed within 28 days of Day 1. For subject eligibility in the Dose Escalation portion subjects need only have evaluable disease (evaluable disease may include measurable lesions, although not required, but also may include such lesions as bone metastasis or pleural effusions that can't be measured but can be evaluated). For subject eligibility in the Dose Expansion portion measurable disease must be determined using RECIST v1.1 (Eisenhauer 2009; Appendix C).

During the study, CT/MRI scans for objective tumor assessment (based on RECIST v1.1 and irRC) will be performed at the end of Cycle 2, at the end of Cycle 4, and at the end of every fourth treatment cycle thereafter (i.e., Week 3 of Cycles 2, 4, 8, 12, 16 and beyond). CT/MRI scans should be performed after the last dose in each cycle to allow time for reading of the scans by the Investigator prior to start of subsequent cycles. For subjects who are withdrawn from the study due to clinical disease progression, a CT/MRI scan should be requested as soon as possible. At the End of Treatment Visit, a CT/MRI scan is only required if radiographic disease progression was not documented in the previous CT/MRI scan.

Note: For disease assessment, if a CT/MRI scan is taken at screening then the same modality of scanning must be used for the subject throughout the course of the study.

A CT/MRI brain scan must also be performed at Screening (within 28 days prior to first dose of study drugs), to assess potential CNS disease and/or metastases.

For the duration of the study (i.e., post-baseline), CT/MRI of the brain will be performed if clinically indicated, and within a target of 1 week after a subject achieves a complete response (CR). For NSCLC subjects with a history of treated brain metastases, brain scans will be performed at tumor assessment time points.

Additional optional imaging using PET/CT and DCE-MRI will be performed at selected sites only to assess treatment effects of pembrolizumab based on tumor blood flow and metabolic activity. Details about the conduct of these assessments are provided in a separate manual.

8.2.16. Pharmacokinetic Assessments

Plasma samples will be collected to assess the potential effects of pembrolizumab on the PK of PEGPH20 (as specified in Table 3). Additionally, serum samples will be collected to potentially assess the PK of pembrolizumab as an exploratory endpoint. Post-dose PK time points should be relative to the stop time of the PEGPH20 infusion. If samples are collected from a central line, the line should be flushed with saline prior to collecting the PK samples. Samples should not be collected from the same line used to administer PEGPH20. Actual sampling times must be recorded. Initial testing will be done during the study; however, samples will be stored for possible re-analysis if deemed necessary and for potential future testing of other biomarkers that may be found to be relevant.

If a subject discontinues PEGPH20 therapy, PEGPH20 PK samples will not be collected from that subject. However, if that subject continues on pembrolizumab therapy at the discretion of the Investigator, pembrolizumab PK samples must be collected.

8.2.17. Biomarker Assessments

This study will collect samples for biomarker assessments in all subjects (where not prohibited by local regulations). Sample types collected include tumor samples and plasma samples. Any sample or derivatives (such as deoxyribonucleic acid [DNA], ribonucleic acid [RNA], and protein) may be stored for up to 15 years after study completion to assist in any research related to PEGPH20 or cancer, and for potential diagnostic development.

In addition, biomarkers identified in other clinical studies may also be assessed in the biomarker samples collected from subjects enrolled in this study. The decision to perform other biomarker assessments may be based on the clinical outcome of this study and/or the signals observed in other clinical studies or other information available at that time.

Refer to the Laboratory Manual for detailed instructions on the processing, storage, and shipping of samples.

8.2.17.1.1. Tumor Biopsies

Tumor tissue needs to meet specific tissue sample requirements as follows (see Laboratory Manual):

- A tumor tissue in FFPE block or 5-10 unstained, consecutive core biopsy slides from 1 tumor tissue block are preferred but not mandatory for subjects eligible for the Dose Escalation portion.
- A tumor tissue in FFPE block or 10-15 unstained, consecutive tumor tissue slides
 from 1 tumor tissue block are mandatory for subjects eligible for the Dose Expansion
 portion, that meet specific tissue sample requirements (see Laboratory Manual).
 Archived resection specimens from the primary tumor without radiologic evidence of
 metastasis at the time of resection are not suitable to establish histological
 confirmation and require new tumor tissue of a metastatic site.
- Fine needle aspiration and/or brushing biopsy are not acceptable.

The pathology report as well as any molecular pathology reports (e.g., for ALK or EGFR mutational status in NSCLC and HER2 status in gastric cancer) must be provided. Specific sampling and processing instructions will be outlined in a separate laboratory manual. The tumor biopsy, whether a block or unstained slides, must be sent to the appropriate laboratory as soon as possible after it is obtained; however, it should not be sent prior to the subject signing the ICF (or prescreening ICF if used in Dose Expansion). Tumor biopsy samples will be utilized for analysis of HA, PD-L1 expression levels (retrospectively), and other exploratory biomarkers.

An optional post-dose biopsy will be collected at the end of Cycle 1 for all subjects who provide separate informed consent. The sample will be analyzed for tumor HA, PD-L1 expression, and other exploratory biomarkers in comparison with the pre-dose sample to evaluate PEGPH20 and/or pembrolizumab effects.

8.2.17.1.2. Plasma Hyaluronan and Exploratory Biomarkers

Plasma HA is an indicator of PEGPH20 pharmacological activity. Baseline and post-dose HA levels in plasma samples will be analyzed to evaluate the PEGPH20 treatment effect, and assess

drug exposure. In addition, plasma samples may be analyzed for exploratory biomarkers of PEGPH20 and/or pembrolizumab activity.

8.2.17.1.3. Tumor-Associated Hyaluronan and Tissue-Based Biomarkers

Tumor tissue available at Screening and collected optionally during the study will be sent to a central laboratory and tested for HA levels using a co-developed investigational diagnostic assay (VENTANA RxDx). This assay uses an affinity-histochemistry-based staining method to evaluate HA levels in tumor biopsies.

Expression of exploratory biomarkers will also be assessed.

For screening purposes, the result for each subject screened (i.e., eligible/ineligible based on HA level) will be sent to the sites to determine eligibility of subjects to enter the study.

8.2.17.1.4. Tumor-Associated PD-L1 Expression in Gastric Adenocarcinoma

Tumor tissue available from gastric adenocarcinoma subjects at screening and collected optionally during the study will be tested for PD-L1 expression levels retrospectively.

8.2.17.1.5. Tumor-Associated PD-L1 expression in NSCLC

Tumor tissue available from NSCLC subjects at screening and collected optionally during the study will be tested retrospectively for PD-L1 expression levels.

8.3. Study Drug Administration

Each treatment cycle is 21 days (3 weeks).

In Dose Escalation, PEGPH20 will be administered on Day 1, Day 8 and Day 15 of each 21-day cycle (i.e. 3 doses/cycle) and pembrolizumab (2 mg/kg every 21 days) on Day 1 of each cycle (i.e. 1 dose/cycle), 4-6 hours after the completion of PEGPH20 administration.

In Dose Expansion, PEGPH20 will be administered on Day 1, Day 8 and Day 15 of each 21-day cycle (i.e. 3 doses/cycle) and pembrolizumab (200 mg every 21 days) on Day 1 of each cycle (i.e. 1 dose/cycle), 4-6 hours after the completion of PEGPH20 administration.

Treatment in both portions of the study will continue until disease progression or unacceptable toxicity, death, or withdrawal of consent from the study.

If a dose of PEGPH20 is missed on Day 1 of cycle 2 or beyond, the cycle will continue as scheduled. If it is known that pembrolizumab will be missed or held on Day 1, PEGPH20 should also be held and the cycle will not start until the first dose of pembrolizumab is administered. This will require planning such that the dose of PEGPH20 can be given before the pembrolizumab dose is set to resume.

8.3.1. PEGPH20

8.3.1.1. PEGPH20 Administration

The PEGPH20 dose will be individually calculated for all dosing visits according to the subject's screening weight. In calculating the dose, there will be no downward adjustment to "ideal" body weight. Doses should be re-adjusted if the subject's weight changes by >10%. If the subject's weight changes by $\le 10\%$, no adjustment is necessary unless the site has a standard procedure to adjust doses based upon current weight. The dispensing pharmacist will verify the dose accuracy with a qualified study staff member. The appropriate dose will be diluted as per the instructions provided in a separate pharmacy manual.

After completion of pre-dose activities, PEGPH20 will be administered as an IV infusion over 10 minutes, approximately 1 mL/minute (a window of +2 minutes is allowed, i.e., infusion can be 10 to 12 minutes), under observation by qualified clinic staff. The volume and/or duration of PEGPH20 administration may change at the discretion of the Sponsor, based upon safety information. The study nurse or alternate designee by the Investigator will record the time the infusion was started and stopped. A saline flush should follow IV delivery of the complete PEGPH20 dose as per standard of care for flushing IV lines. Only a peripheral line should be used for the administration of PEGPH20 (heparin flushes should not be used on the same line as PEGPH20), but heparin flushes may be used for central lines as per standard of care. In the event that peripheral venous access cannot be obtained, the central line may be used. If this happens, ensure the line is flushed with saline (minimum of 10 mL) prior to administering PEGPH20 and after administering PEGPH20. Ensure the PEGPH20 administration is not done immediately before or after the central line has been flushed with a heparin flush (i.e., ensure the line is flushed with a heparin flush no earlier than 1 hour before or after the PEGPH20 administration).

8.3.1.2. Hypersensitivity to PEGPH20

In the event of a hypersensitivity reaction, the PEGPH20 infusion should be stopped and the symptoms should be treated as necessary. Halozyme should be contacted immediately (see study manual for contact information).

At the Investigator's discretion and after discussion with the Sponsor, a re-challenge for the next visit may be done if the reaction is not considered anaphylaxis and is \leq Grade 2. Any subject with anaphylaxis or a \geq Grade 3 hypersensitivity reaction/infusion reaction should be discontinued from the study. In the event of a \leq Grade 2 hypersensitivity/infusion reaction, the Sponsor and Investigator will agree on how subsequent injections will be administered. In general, a re-challenge should be done after pre-medication with a combination of IV diphenhydramine, IV H2 blockers (such as famotidine), and IV dexamethasone. If the hypersensitivity reactions are experienced at the re-challenge, the subject should be discontinued from the study.

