8.3.1.3. PEGPH20 Dose Modification Guidelines

PEGPH20 dose adjustments are allowed based on toxicities that are deemed related, possibly related, or probably related to PEGPH20. See Table 6 for guidelines.

Table 6: PEGPH20 Dose Adjustment and Toxicity Management Guidelines

Event	Management/Action
Musculoskeletal	
Any Grade 1 MSEs	• No change in PEGPH20 dose or frequency. Prescribed medication such as narcotics, muscle relaxants and other analgesics (with the exceptions of steroids), OTC drugs and physical therapy can be used at the Investigator's discretion.
Any Grade 2 MSEs	Based on Investigator's discretion use prescribed medication such as narcotics, muscle relaxants and other analgesics (with the exceptions of steroids), OTC drugs and physical therapy.
	• If the MSEs resolve or decrease to Grade 1 with administration of prescribed medication such as narcotics, muscle relaxants and other analgesics (with the exceptions of steroids), OTC drugs and physical therapy, PEGPH20 can be continued.
	• If the MSEs persist at Grade 2 despite administration of prescribed medication such as narcotics, muscle relaxants and other analgesics (with the exceptions of steroids), OTC drugs and physical therapy, the Investigator must discuss any further PEGPH20 treatment with the Sponsor's Medical Monitor.
Any Grade 3 or 4 MSEs	Hold PEGPH20 treatment.
	Based on Investigator's discretion use prescribed medication such as narcotics, muscle relaxants and other analgesics (with the exceptions of steroids), OTC drugs and physical therapy.
	• If the MSEs decrease to ≤ Grade 2, the Investigator must discuss any PEGPH20 treatment reinitiation with the Sponsor's Medical Monitor.
	• If the MSEs persist at Grade 3 or 4 levels, PEGPH20 should not be resumed.

Table 6: PEGPH20 Dose Adjustment and Toxicity Management Guidelines (Continued)

Event	Management/Action		
All non-MSE Events (Except TE Even	ts) Potentially Related to PEGPH20		
Grade 1 or 2	No change in PEGPH20 treatment.		
Grade 3	• Hold PEGPH20 treatment.		
	• If toxicity is resolved to baseline within 14 days, treatment may resume at the same dose level.		
	• If toxicity is reduced to ≤ Grade 2 within 14 days, treatment may resume but at next lower dose but must be discussed and decided upon mutual agreement with the Sponsor's Medical Monitor.		
	• If toxicity persists at Grade 3, any consideration to resume PEGPH20 treatment must be discussed with the Sponsor's Medical Monitor.		
Grade 4	Hold PEGPH20 treatment.		

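### Table 6's dose rules for PEGPH20-related non-musculoskeletal events do not exclude hypersensitivity/infusion reactions, and at Grades 1-2 and Grade 3 they contradict Protocol Section 8.3.1.2

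*Protocol*

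**What the plan says.** Protocol Section 8.3.1.2 deals specifically with hypersensitivity to PEGPH20.

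- For any such reaction: "In the event of a hypersensitivity reaction, the PEGPH20 infusion should be stopped and the symptoms should be treated as necessary", and "Halozyme should be contacted immediately".
- At Grade 2 or lower, and if the reaction is not anaphylaxis, the Investigator may re-challenge at the next visit once the Sponsor has been consulted. Moreover, "the Sponsor and Investigator will agree on how subsequent injections will be administered", generally with pre-medication.
- On recurrence: "If the hypersensitivity reactions are experienced at the re-challenge, the subject should be discontinued from the study".
- The removal rule applies to anaphylaxis and to any reaction at or above the level named here: "Grade 3 hypersensitivity reaction/infusion reaction should be discontinued from the study".

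Section 8.3.1.3 follows directly and contains Table 6. Its second block opens "All non-MSE Events (Except TE" (the bracket closes after the word Events) and is limited to events potentially related to PEGPH20.

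- Grade 1 or 2: "No change in PEGPH20 treatment".
- Grade 3: hold, then three entries. The first is "If toxicity is resolved to baseline within 14 days, treatment may resume at the same dose level". The second allows a restart at the next lower dose, agreed with the Medical Monitor, if the event falls to Grade 2 or lower within 14 days. The third says that if Grade 3 persists, resumption has to be discussed with the Medical Monitor.
- Grade 4: hold. If the event resolves or falls to Grade 2 or lower, re-initiation has to be discussed.

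**The concern.** A PEGPH20 hypersensitivity or infusion reaction is drug-related, is not a musculoskeletal event (MSE) and is not a TE event, so it falls inside the second block of Table 6 as worded. TE events are excepted and given their own row; hypersensitivity reactions get neither. The table's closing notes point to Sections 10.12.1 to 10.12.3 but not to 8.3.1.2, and neither section says which prevails.

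A site that uses Table 6 as its working chart would therefore find written permission to give PEGPH20 again after a Grade 3 reaction for which the preceding section removes the subject. It would also find an instruction to change nothing after a milder reaction that the preceding section manages jointly with the Sponsor.

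There is a smaller consequence for reporting. A restart could comply with Table 6 and breach 8.3.1.2. Protocol Section 12.1.2 lists failure to follow the protocol among its examples of major deviations, and SAP Section 4.5 summarizes major deviations, so the classification of such a restart would be unclear.

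**Working it through.** No stated figure is involved, so the check is a comparison of the two texts, applying each Table 6 entry to a hypersensitivity/infusion reaction.

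| Reaction | Table 6, non-MSE block | Section 8.3.1.2 | Relation |
|---|---|---|---|
| Grade 1-2 | No change | Stop infusion; contact Sponsor; re-challenge only after Sponsor discussion and if not anaphylaxis; pre-medication in general; discontinue on recurrence | Contradiction |
| Grade 3, back to baseline within 14 days | Same-dose restart permitted; no Medical Monitor step in this entry | Discontinue from study | Contradiction |
| Grade 3, down to Grade 2 or lower within 14 days | Next-lower-dose restart permitted by agreement with Medical Monitor | Discontinue from study | Contradiction |
| Grade 3, persistent | Any resumption must be discussed | Discontinue from study | Looser, can be reconciled |
| Grade 4, resolved or down to Grade 2 or lower | Any re-initiation must be discussed | Discontinue from study | Looser, can be reconciled |

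**Count.** The block has 1 + 3 + 1 = 5 entries. One directs no change, two permit a restart and two require discussion only. The contradictory entries number 1 + 2 = 3, in two grade bands (Grades 1-2 and Grade 3). The other two can be satisfied together with 8.3.1.2, because a discussion may end in discontinuation. Grade 4 that does not improve is simply held under Table 6, with no further instruction. These are counts of table entries, not an effect size.

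**Grade 1-2.** Stopping the infusion could be read as acute management, and the table's no-change entry as referring only to later dosing. That does not remove the conflict. 8.3.1.2 also governs later dosing: Sponsor discussion first, an agreed manner of administration, pre-medication as a rule, and removal if the reaction recurs.

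**Grade 3.** The same-dose entry matters most, because it is a permission with no Medical Monitor step. Section 8.3 plans PEGPH20 on Days 1, 8 and 15 of a 21-day cycle, so the next cycle begins on Day 22. The gaps are 8 - 1 = 7, 15 - 8 = 7 and 22 - 15 = 7 days. Since 7 is less than 14, a Grade 3 reaction on Day 1 that is back to baseline by Day 8 already meets the table's restart condition at the next planned dose.

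**Comparison within the protocol.** The definition of dose-limiting toxicity (Synopsis and Section 6.1.1) expressly leaves out hypersensitivity/infusion reactions. The protocol thus makes that exclusion in words where it wants it; Table 6 has no such words.

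**The case against.** The strongest reply is that nothing is really in conflict. 8.3.1.2 is devoted to this topic, is directive, and immediately precedes a general table presented as guidelines. On ordinary reading the specific governs the general. The dose-limiting toxicity definition supports this: it explains that these reactions are generally unrelated to dose level, which is a reason to keep them out of a dose-adjustment table. Immediate Sponsor contact is required for any hypersensitivity reaction, so a site would have to overlook both that step and the removal rule before reaching a Day 8 restart. Finally, a permission to resume is not breached by discontinuing.

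Most of this stands as a limit on the practical risk. It does not remove the inconsistency. The protocol states no precedence, and a permission in one section for what another section rules out is still a contradiction for a site deciding whether it may dose.

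A reader might go further and infer that the two sections conflict at every grade. The documents do not support that. The entries for persistent Grade 3 and improved Grade 4 grant no permission, and a discussion that ends in discontinuation satisfies both texts. Nor do the documents support an inference that any subject was re-exposed after a severe reaction; they report no such case.

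**Conclusion.** The point holds for two grade bands: Grades 1-2, where no change is directed against a stop-and-consult rule, and Grade 3, where a restart is permitted against removal from the study. It rests on the literal scope of the block heading and on the absence of any precedence statement or cross-reference.

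The issue is minor and concerns safety conduct. It is worth correcting because a stated rule, taken at face value, gives the wrong action for a patient-safety event. The incidence of such reactions is not given, so the number of subjects affected cannot be stated. SAP Section 4.7.2 records the decision of 31 May 2018 to stop further enrollment, so only subjects dosed under this text are concerned. Sample size, power and the ORR test do not depend on it.

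**What to change.** In Table 6, extend the exception in the heading of the second block. After TE Events, inside the bracket, add: *and Hypersensitivity/Infusion Reactions; see Section 8.3.1.2*. Leave the rest of the heading, the entries below it and Section 8.3.1.2 unchanged, so that 8.3.1.2 governs these reactions at every grade.

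The cost is one line in one table heading. Policy, procedures, data collection and analysis stay as they are.
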